We will specifically exclude pediatric ankle fractures in children under 18 years-of-age, tibial plafond (pilon) fractures in children and adults, medial malleolar osteotomies to access the talus, perform an ankle fusion, or deal with a pathologic lesion, osteonecrosis, or infection due to their diversity in diagnosis, management, and weight bearing status. Patients with prior surgical treatment of the ankle for fracture, deformity, infection, neoplasia, or other pathologic process on the ipsilateral extremity will also be excluded.

Patients that are non-weight bearing on one or both lower extremities prior to sustaining their ankle injury will be excluded.

Randomization

All elective and emergent admissions to Stanford Hospital and Clinics and Kaiser Permanente – South Sacramento that meet our inclusion/exclusion criteria will be identified and solicited for consent. Patients will be randomized by sealed envelope to surgical fixation with traditional headed screws, plates, and wires or Acutrak headless compression screws. At the time of randomization, the fracture pattern and severity, past medical history and medications, and demographic data will be documented.

Follow-up Protocol

After operative fixation, patients will receive fracture follow-up with a clinical evaluation for tenderness, radiographs to evaluate stability and union at 2 weeks, 6 weeks, 3 months of surgery and complete the PROMIS and VAS pain scores. Patients will be followed by telephonically once the fracture union is confirmed radiologically by the operating surgeon at 6 months, 1 year, and 2 years after surgical fixation. The VAS pain scores will be administered telephonically and the PROMIS questionnaires will be mailed to the patients (Table 1).⁹

Table 1: Protocol Summary

Time and Event Table	Injury/Office	2 weeks	6 weeks	3 months	6 months (over Telephone & mail)	1 year (over Telephone & mail)	2 years (over Telephone & mail)
Discuss Study	X						
Screening Log	X						
Informed Consent	X						
Eligibility Worksheet	X						
Demographic Data	X						
Medical History	X						
Randomization	X						
Clinical Assessment							
•Medial Ankle Tenderness	X	X	X	X	X	X	X
•Lateral Ankle Tenderness	X	X	X	X	X	X	X
Patient Reported Outcomes							
•PROMIS Score	X	X	X	X	X	X	X
•VAS Pain (by location)	X	X	X	X	X	X	X
•On Narcotics (yes/no)	X	X	X	X	X	X	X
Radiographs							
•Anterior-to-Posterior Ankle	X	X	X	X	-	-	-
•Lateral Ankle	X	X	X	X	-	-	-
Operative/Device	X						

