Removal of Hardware		X	X	X	X	X	X
Adverse Event	X	X	X	X	X	X	X
End of Study							X

Criteria for Removal of Hardware

Hardware may be removed if there is a surgical indication or patient/surgeon preference for removal. Patients will be asked whether they feel bothersome sensitivity at the both medial and lateral malleolus. If they mention sensitivity to light touch that is not bothersome they should not be subjected to hardware removal unless by patient or surgeon preference and noted as medial or lateral hardware removed for preference. On the other hand, if they mention bothersome sensitivity, it would be rated on a 0-5 Likert intensity scale. All bothersome sensation will be subjected to hardware removal and noted as removal for sensitivity. Other reasons for hardware removal indications include infection and non-union or mal-union requiring revision open reduction and internal fixation. The location of symptoms and reason for hardware removal should be specified and documented.

Documentation of Fracture Union

Union will be defined as a pain free fracture site on examination with evidence of radiographic healing and a return to full weight bearing confirmed by the operating surgeon

Power Analysis and Statistics

Retrospective review of ankle hardware removal cases indicates that 6% (8/126) of patients have their hardware removed for non-pain issues (e.g., infection, etc.) at 6 months and 17% (22/126) of patients have their hardware removed for pain on the medial or lateral side of the ankle at 6 months.⁸ Hence, the overall rate of hardware removal is 24% but if we can reduce half of the medial hardware removals the overall rate would be 14.5%. To detect this 9.5% difference, it would take 424 randomized patients (alpha = 0.05, and 80% power). Medial hardware removal will be prohibited for lateral hardware pain.

Utilizing the STRIDE database available at Stanford University, there have been 155 procedures involving fixation of the medial malleolus (CPT: 27766, 27814, 27822, 27823) over the past three years. Assuming a similar procedure burden at the other major Level I Trauma center and extrapolating this three-year data, we estimate the capability to enroll 500 patients over three years.

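### The removal rule for bothersome sensitivity has no condition on healing or persistence, so on its face it reaches patients whose union is still being assessed

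*Combined protocol and SAP*

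**What the plan says.** All references are to the Combined protocol and SAP.

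**Criteria for Removal of Hardware.** The section opens in permissive terms: "Hardware may be removed if there is a surgical indication or patient/surgeon preference for removal". It then splits sensitivity into two classes. For patients whose sensitivity does not bother them, "they should not be subjected to hardware removal unless by patient or surgeon preference". For the others, "if they mention bothersome sensitivity, it would be rated on a 0-5 Likert intensity scale", followed by "All bothersome sensation will be subjected to hardware removal and noted as removal for sensitivity". It continues: "Other reasons for hardware removal indications include infection and non-union or mal-union requiring revision open reduction and internal fixation".

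**Follow-up Protocol.** Patients are seen "with a clinical evaluation for tenderness, radiographs to evaluate stability and union at 2 weeks, 6 weeks, 3 months of surgery". Remote follow-up comes later: "Patients will be followed by telephonically once the fracture union is confirmed radiologically by the operating surgeon".

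**Documentation of Fracture Union.** "Union will be defined as a pain free fracture site on examination with evidence of radiographic healing", together with full weight bearing. The removal criteria do not refer to this definition.

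**Power Analysis and Statistics.** Medial hardware may not be taken out because of pain on the lateral side.

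**Study summary, Study Objectives.** The primary objective includes a lower incidence of medial hardware removal, judged one year from the fracture.

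**The concern.** Fixation is there to hold the fracture until it heals. A rule that sends every bothersome sensation to removal, without asking whether the bone has healed, covers patients whose stability is still under radiographic assessment. Taking fixation out of an unhealed fracture is unsafe.

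There is a second exposure. The rule does not ask whether the symptom lasts. A patient bothered at 2 weeks and comfortable later still falls under a sentence that covers all bothersome sensation, and so could have an operation that is no longer needed. Such a removal would also count in the one-year outcome.

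**Working it through.** The plan gives no figure on this point, so the first four steps compare text. The arithmetic in step 5 concerns only what the fix would do to timing.

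**1. Does the sentence direct treatment, or only label it?** It has two parts: hardware is removed, and the reason is recorded. The paired instruction for non-bothersome sensitivity uses the same phrase to hold treatment back, with an exception for preference. The bothersome class has no such exception. Labelling is part of the purpose, but the treatment instruction is there too.

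**2. Is there a condition anywhere?**

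| Possible condition | What the text has |
|---|---|
| Healing or union | None; union is defined in the next section but not linked to removal |
| Minimum time after surgery | None |
| Persistence or reassessment | None |
| Intensity | A 0-5 rating, with no cut-off tied to removal |
| Whether bothersome | Yes: non-bothersome sensitivity is excluded unless by preference |
| Location | Yes: no medial removal for lateral pain |

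The two restrictions that exist do not concern healing.

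**3. Is there a period when the rule could meet an unhealed fracture?** Union is an open question at 2 weeks, 6 weeks and 3 months, and planned telephone follow-up starts only after radiological confirmation. The gap therefore lies in the clinic phase. Table 1 schedules tenderness and VAS pain by location at those visits. It has no row for the sensitivity question, and no text says when that question is asked, but nothing postpones it until after healing. The hardware-removal row in Table 1 is probably data capture and is not relied on here.

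**4. Can the frequency be derived?** No. The plan cites 22/126 pain-related removals by 6 months, without their timing inside that window or the healing status at removal.

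**5. How long would a healing condition delay removal?** Assumptions: healing is confirmed at a scheduled radiograph, 3 months = 13 weeks, 1 year = 52 weeks.

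| Sensitivity reported | Healing confirmed | Wait | Time left to one year |
|---|---|---|---|
| 2 weeks | 6 weeks | 6 − 2 = 4 weeks | 52 − 6 = 46 weeks |
| 2 weeks | 3 months | 13 − 2 = 11 weeks | 52 − 13 = 39 weeks |
| 6 weeks | 3 months | 13 − 6 = 7 weeks | 52 − 13 = 39 weeks |

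Visits are counted from surgery and the one-year point from the fracture, so the time left is shorter by the injury-to-surgery interval, which is not given. A deferred removal can still count at one year unless healing comes much later or the symptom resolves.

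**The case against.** The strongest case against is that the protocol does not order early removal. The sentence sets no deadline: a surgeon who records bothersome sensitivity at 2 weeks and removes the hardware after union has complied with it. The section opens with *may*, and the phrase introducing infection and non-union as other reasons makes sensitivity one indication among several, arguably under that same discretion. Both paired sentences end in a recording instruction, which fits a scheme for classifying reasons. The visits for the sensitivity question are not stated, and no surgeon is likely to strip fixation from an unhealed ankle.

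Much of this stands. A reader might infer that the protocol requires removal before healing and leaves the surgeon no basis to defer. The documents do not support that: no deadline is set, and *may* leaves room for judgement. A reader might also infer a bias between arms, or an effect on the union comparison or the sample size. The documents give nothing from which to derive any of these.

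What does not fall is the gap itself. Discretion under *may* sits in tension with a sentence that says all such sensation *will* go to removal, and neither supplies a healing condition. Deferral alone also does not help the patient whose symptom resolves, because the rule does not ask whether it is still present.

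The objection also notes limits of the remedy. The indication and preference route stays open before healing, removal stays mandatory at every intensity afterwards, and the protocol states no criteria for radiographic healing. These points are fair, but none makes the amended sentence less safe than the current one.

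**Conclusion.** The concern holds in a limited form. The rule directs removal for all bothersome sensitivity with no condition on healing, persistence or intensity. Deferral is possible, but as written the rule allows, and on its face directs, removal while union is still being evaluated (2 weeks to 3 months), and removal for early sensitivity that later resolves.

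The size of the problem is unknown. The conclusion rests on reading the sentence as a treatment instruction as well as a recording one, which the pairing supports, and on nothing in the documents holding the sensitivity question back until healing. It is worth correcting because the possible harm is to patients and the remedy is small. Confidence is medium, given the tension between *may* and *will*.

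**What to change.** Amend the one sentence to this effect: *Once the operating surgeon has confirmed radiographic healing, hardware will be removed for bothersome sensation that is still present, with sensitivity recorded as the reason; before then the sensation will be recorded and reassessed.* Infection, non-union and mal-union keep their separate removal reasons.

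The condition should be radiographic healing and not the full union definition. That definition requires a pain-free site, which could bar removal for true hardware pain.

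Costs:

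- No added scheduled visits, radiographs or patients.
- Patients with bothersome sensitivity before healing wait, by the 4 to 11 weeks worked out above in the scheduled-visit cases.
- The timing of removals that feed the primary objective would depend on the operating surgeon's healing judgement, and no blinding of that surgeon is described.
- Patients not healed at 3 months need a later radiograph. Table 1 schedules none after that visit, but the follow-up text already implies one, because telephone follow-up waits for radiological confirmation.

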The fixation provided by the Acutrak headless compression screws provide sufficient fixation to achieve union and a favorable clinical outcome in both horizontal and vertical medial malleolus fractures when compared to bicortical and unicortical screw fixation, tension band wiring, and mini-fragment or buttress plating. However, minimizing the amount of dissection required for implantation as well as lack of prominent hardware surfaces will reduce the incidence and severity of hardware related pain and correspondingly the necessity of hardware removal.

Specific Aims

- 1) *Prospectively establish equivalence with respect to fracture union rate after Acutrak headless compression screw fixation when compared to other fixation methods for medial malleolus fractures.*
- 2) *Prospectively establish equivalence with respect Patient Reported Outcome Measurement Information System (PROMIS) scores after Acutrak headless compression screw fixation when compared to other fixation methods for medial malleolus fractures.*
- 3) *Prospectively establish superiority with respect to hardware related pain after Acutrak headless compression screw fixation when compared to other fixation methods for medial malleolus fractures.*
- 4) *Prospectively establish superiority with respect to the hardware removal rate after Acutrak headless compression screw fixation when compared to other fixation methods for medial malleolus fractures.*

Study Design

Institutional Review Board and HIPAA

The institutional review boards of Stanford Hospital and Clinics and the Kaiser Permanente Hospital, South Sacramento will review and approve this study prior to initiation. All patient information will be kept confidential in accordance with HIPAA and only the study coordinator and the protocol director will have access to the data.

Inclusion/Exclusion Criteria

All ankle fractures that undergo open reduction internal fixation of the medial malleolus in adults at or over 18 years-of-age will be considered for inclusion.

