Intended Use	The Acutrak headless compression screws are intended to provide fixation and anatomically reduce fractures of the medial malleolus that occur via supination-external rotation, pronation-external rotation, or pronation-abduction resulting in an oblique fracture pattern as well as supination-adduction resulting in a vertical shear fracture pattern.
Study Purpose	The fixation provided by the Acutrak headless compression screws provide sufficient fixation to achieve union and a favorable clinical outcome in both horizontal and vertical medial malleolus fractures when compared to bicortical and unicortical screw fixation, tension band wiring, and mini-fragment or buttress plating. However, minimizing the amount of dissection required for implantation as well as lack of prominent hardware surfaces will reduce the incidence and severity of hardware related pain and correspondingly the necessity of hardware removal.
Study Objectives	
Primary:
 
 • A successful outcome would be a reduction in the rate or severity of hardware related pain localized to the medial malleolus reducing the incidence of hardware removal from the medial malleolus at one year after sustaining an ankle fracture.
	
Secondary:
 
 • Another successful outcome would be an equivalent radiographic and clinical union rate when compared to traditional fixation methods. • Another successful outcome would be an equivalent PROMIS scores when compared to traditional fixation methods.

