Number of Subjects	Utilizing the STRIDE database available at Stanford University, there have been 155 procedures involving fixation of the medial malleolus (CPT: 27766, 27814, 27822, 27823) over the past three years. Assuming a similar procedure burden at another major Level I Trauma center at Kaiser Permanente Hospital, South Sacramento and extrapolating this three-year data, we estimate the capability to enroll and randomize over 500 patients requiring medial malleolus fixation over three years between the three centers.
Number of Sites	Three Level I Trauma Centers will participate: 
 • Stanford Hospital and Clinics • Kaiser Permanente – South Sacramento • Brigham and Women's Hospital- Boston
Procedure Schedule	See Table 1
Subject Duration	The estimated duration for each subject is 2 years. Subjects are released from postoperative follow-up after post-operative observation for two years.
Study Duration	The estimated duration of the study is 5 years: 3 years for enrollment and 2 year for postoperative follow-up for each enrolled subject.
Safety	All adverse events and complications will be continuously monitored throughout the study. The type and frequency will be analyzed by a medical monitor.
Statistical Methods	All continuous variables will be reported as the mean and errors are reported as standard deviation. All categorical variables will be reported as the subset number and percentage of the total. Comparisons will be performed with the appropriate statistical test when indicated. Statistical significance will be set at p less than 0.05 with an appropriate Bonferroni correction for multiple comparisons when indicated.

References

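### The 9.5-point design effect mixes counts with rounded percentages and names a medial count that is not given; if pain removals are halved, the counts give at most 8.7 points and 424 patients give at most about 74% one-sided power

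*Combined protocol and SAP*

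**What the plan says.** The section Power Analysis and Statistics starts from a retrospective series of 126 patients and gives two counts:

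- non-pain removals: "6% (8/126) of patients have their hardware removed for non-pain issues (e.g., infection, etc.) at 6 months";
- pain removals: "17% (22/126) of patients have their hardware removed for pain on the medial or lateral side of the ankle at 6 months".

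It concludes that "the overall rate of hardware removal is 24" per cent, and then that "if we can reduce half of the medial hardware removals the overall rate would be 14.5" per cent. The sample size follows: "To detect this 9.5% difference, it would take 424 randomized patients (alpha = 0.05, and 80% power"). The section gives no count of medial removals, no sidedness and no allocation ratio.

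The Hypothesis section gives the mechanism: less dissection and less prominent hardware "will reduce the incidence and severity of hardware related pain and correspondingly the necessity of hardware removal". In the study summary table, the primary objective concerns "reducing the incidence of hardware removal from the medial malleolus at one year after sustaining an ankle fracture".

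**The concern.** The three figures that drive the sample size (24%, 14.5%, 9.5 points) are presented as following from 8/126 and 22/126. Two things stand in the way.

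1. The two rates appear to come from different arithmetic. The baseline agrees with the counts but not with the sum of the printed percentages. The treatment rate agrees with the printed percentages but not with the counts.
2. The sentence halves medial removals, but the only pain count covers medial and lateral removals together. Halving a subset of the 22 cannot remove more than halving all 22.

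This is the plan's only sample size justification. If the effect is overstated, so is the 80% power claimed for 424 patients.

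**Working it through.** **Inputs** (Power Analysis and Statistics): 8/126 non-pain removals; 22/126 pain removals, medial or lateral; alpha 0.05; power 80%; total 424. The two counts are taken as non-overlapping, as the plan's 24% implies. Assumed because unstated: 1:1 allocation, so 212 per arm.

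**Step 1. Where the rates come from.**
- Baseline from counts: (8 + 22)/126 = 30/126 = 23.8%, printed as 24%. The printed percentages would give 6 + 17 = 23%.
- Treatment rate from printed percentages: 6 + 17/2 = 14.5%. The counts would give (8 + 11)/126 = 19/126 = 15.1%.
- As printed: 24 − 14.5 = 9.5 points.
- Counts throughout: 23.8 − 15.1 = 11/126 = 8.7 points.
- Printed percentages throughout: 23 − 14.5 = 8.5 points.

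**Step 2. Reproducing 424.** Pooled two-proportion z-test without continuity correction, with p̄ = (p1 + p2)/2:

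n per arm = {z_α √[2p̄(1 − p̄)] + z_β √[p1(1 − p1) + p2(1 − p2)]}² / (p1 − p2)²

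With p1 = 0.24, p2 = 0.145 and p̄ = 0.1925, the two square roots are 0.5576 and 0.5535.
- One-sided 5%: {1.645 × 0.5576 + 0.842 × 0.5535}² / 0.095² = 211.9, so 212 per arm and 424 in total. This is the plan's figure.
- Two-sided 5%: 269.2, so 270 per arm and 540 in total.

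The one-sided test is therefore used below.

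**Step 3. Power at 424 if pain removals are halved.**

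Power = Φ({(p1 − p2)√n − z_α √[2p̄(1 − p̄)]} / √[p1(1 − p1) + p2(1 − p2)])

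With p1 = 30/126, p2 = 19/126 and n = 212: (0.0873 × 14.56 − 1.645 × 0.5597)/0.5563 = 0.63, and Φ(0.63) = 73.6%.

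| Rates | Effect (points) | Power at 424, one-sided | Power at 424, two-sided | Total for 80%, one-sided |
|---|---|---|---|---|
| 24% vs 14.5% (as printed) | 9.5 | 80.0% | 70.0% | 424 |
| 30/126 vs 19/126 (counts) | 8.7 | 73.6% | 62.3% | 508 |
| 23% vs 14.5% (printed percentages) | 8.5 | 72.6% | 61.2% | 520 |

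The 8.7 points is a ceiling on this reading, reached only if all 22 pain removals were medial. Each lateral one takes off 0.5/126 = 0.4 points.

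**Step 4. The other reading: medial removals of any cause are halved.**
- Ceiling, all 30 medial: 15/126 = 11.9 points.
- Medial count needed for 9.5 points: 0.095 × 2 × 126 = 23.9, so about 24 of 30. Only 22 were for pain, so at least 24 − 22 = 2 of the 8 non-pain removals would have to be medial and among those halved.
- 24 of 30 medial: 9.5 points, 80% one-sided power at 424. 23 of 30: 9.1 points, 77%.

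**Step 5. 14.5% taken as a target.** From the counts, 30/126 − 0.145 = 9.3 points. As a share of pain removals this is 0.0931/(22/126) = 53%. One-sided power at 424 is 78.7%.

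**The case against.** The strongest reply is that the sentence can be read so that it holds. It halves medial removals without saying that they are pain removals, and if about 24 of the 30 were medial the 9.5 points is right. The split may exist in the cited source, which is not available here. This stands in part: the any-cause reading cannot be excluded. But no count in the documents supports it. Moreover, 14.5 equals 6 + 8.5, which leaves the non-pain removals untouched, and the Hypothesis section gives pain as the mechanism. Both point to pain removals.

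A second reply is that 14.5% is a conditional target, and a design effect is a choice. Sizing for 24% against 14.5% is internally valid, and 424 reproduces. That stands too, but the plan presents 14.5% as the result of halving, not as a choice. If it is a target, it should be labelled as one.

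Third, the unstated sidedness costs more than this slip: on the plan's own rates, a two-sided test has 70% power at 424. That is correct. It is a separate omission and does not repair the effect size.

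A reader might also infer several stronger conclusions that the documents do not support:
- **That 9.5 points is impossible.** It is not; see Step 4.
- **That the true effect is far below 8.7 points because many pain removals were lateral.** The documents do not give the lateral number.
- **That the primary objective is underpowered.** The figures are overall removal rates at 6 months, while the objective is medial removal at one year. Power for it cannot be derived from them in either direction.
- **That enrolment will fall short.** The Number of Subjects row says "we estimate the capability to enroll and randomize over 500 patients requiring medial malleolus fixation over three years between the three centers". With 500 analysed, 30/126 against 19/126 has 79.6% one-sided power, although this is a capacity estimate and not a commitment.

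**Conclusion.** The concern holds in a limited form. The 9.5-point effect is not derived consistently from the figures beside it, and the medial count that the sentence relies on is not given. That much needs no assumption about the test.

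The power loss is conditional. It requires that pain removals are the events halved, which is the better supported reading, and that the test is one-sided at 5% with 1:1 allocation, which is inferred only because it reproduces 424. On those terms the effect is at most 8.7 points and power at 424 is at most about 74%, a loss of about 6 percentage points from the stated 80%. On the any-cause reading there may be no loss, but that rests on a count the plan does not show. Confidence is high in the arithmetic and moderate in the power loss. The point should be fixed, but it does not show that the trial is mis-sized for its printed target.

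**What to change.** Adopt one of three corrections in Power Analysis and Statistics:

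1. Replace the rates with those from the counts, 23.8% against 15.1% (8.7 points), and restate the power of 424 as about 74% one-sided at best.
2. Print the medial count used, say whether it covers pain removals or removals for any cause, and derive the effect as that count/(2 × 126).
3. Label 14.5% as a chosen target, equal by counts to about a 53% cut in all pain removals (9.3 points, about 79% one-sided power at 424).

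In each case, state the sidedness and allocation ratio, restate the power to match, and say that the figure applies to overall removal at 6 months and not to the primary objective of medial removal at one year.

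The cost is a corrected sentence and a recalculated power statement. The drawback is a less favourable stated power under options 1 and 3, and possibly under option 2. Enrolment and conduct do not change.

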All continuous variables will be reported as the mean and errors are reported as standard deviation. All categorical variables will be reported as the subset number and percentage of the total. Comparisons will be performed with the appropriate statistical test when indicated. Statistical significance will be set at p less than 0.05 with an appropriate Bonferroni correction for multiple comparisons when indicated.

Budget

The vast majority of the budget will go toward an experienced fulltime clinical research coordinator, level II (CRCII, Table 2). This person is critical to our success. Appropriately, some funds will be devoted to insuring the proper training and certification for the CRCII involved in this project as well as supply adequate computing power and meet secure data storage needs. Some funds would be used by the principal investigator and co-investigators to offset local travel and travel to national and international meetings to present the findings of this interdisciplinary work, including the American Academy of Orthopaedic Surgeons (AAOS), the Orthopaedic Trauma Association (OTA), and the American Orthopaedic Foot and Ankle Society (AOFAS).

Table 2: General Budget

Expense			Effort	Cost
Personnel	Principal Investigator	[name]	10%	\$36,000/year
	Co-Investigator	[name]	3%	\$10,000/year
	Co-Investigator	[name]	3%	\$10,000/year
	Co-Investigator	[name]	3%	\$10,000/year
	Co-Investigator	[name]	3%	\$10,000/year
	Co-Investigator	[name]	3%	\$10,000/year
	CRCII	TBD: Stanford	100%	\$90,000/year

	CRCII	TBD: 3 rd center	75%	\$68,000/year
	CRCII	TBD: Kaiser	75%	\$68,000/year
Equipment	Computers			\$3,000/year
	Secure Storage			\$1,000/year
Training				\$5,000/year
Travel	Society Meetings			\$5,000/year
	Between Sites			\$5,000/year
				\$275,000/year

Acumed Study Summary	
Company	Stanford University
Title	Prospective, multi-center, randomized, controlled study evaluating the union rate, rate of medial malleolus hardware removal and clinical outcomes after medial malleolus fracture fixation with Acutrak headless compression screws
Short Title	Acutrak Fixation of Medial Malleolus Fractures
Protocol Number	
Treatment Device	Acutrak headless compression screws
Control Device(s)	Mini-fragment Plating, Antiglides Plating, Headed Unicortical Screws, Headed Bicortical Screws, Tension Band Wiring

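### Alpha has no stated side: 424 patients give 80% power for 24% versus 14.5% only with a one-sided 5% test; two-sided, power is about 70%

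*Combined protocol and SAP*

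**What the plan says.** The only sample-size justification is in Power Analysis and Statistics. It begins from hardware removal for any reason, put at 24% now and at 14.5% if half of the medial removals could be avoided. It then states: "To detect this 9.5% difference, it would take 424 randomized patients (alpha = 0.05, and 80% power".

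The significance rule appears later in the same section and again under Statistical Methods in the Acumed Study Summary: "Statistical significance will be set at p less than 0.05 with an appropriate Bonferroni correction for multiple comparisons when indicated". The test itself is left open. None of these places gives a side, and no other section declares a one-sided test.

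On capacity, the power section says "we estimate the capability to enroll 500 patients over three years". The summary's Number of Subjects entry says "we estimate the capability to enroll and randomize over 500 patients requiring medial malleolus fixation over three years between the three centers". Both are feasibility estimates, not enrolment targets. The Randomization section names two arms but no allocation ratio.

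**The concern.** A two-proportion sample size depends heavily on the side of the test, because the critical value is 1.645 for one-sided 5% and 1.960 for two-sided 5%. When a plan says only alpha 0.05 and p below 0.05, most readers and analysts will take the test as two-sided. If 424 was computed for a one-sided test, the analysis would then run at lower power than the protocol claims.

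Two things are at stake. The first is the chance of missing a real effect of the size the trial was planned to find. The second is that an undeclared side can be chosen after the data are seen. When the result favours Acutrak, a one-sided p of 0.04 is about 0.08 two-sided, so the same data could be called significant or not.

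**Working it through.** **Inputs.** From Power Analysis and Statistics: p1 = 0.24, p2 = 0.145, difference d = 0.095, alpha 0.05, power 80%, total 424. Assumed: 1:1 allocation (212 per arm) and a normal-approximation test without continuity correction.

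**Formula.** Per-arm n = [(z_a·A + z_b·B)/d]², where
- mean proportion = (0.24 + 0.145)/2 = 0.1925
- A = √(2 × 0.1925 × 0.8075) = √0.31089 = 0.5576
- B = √(0.24 × 0.76 + 0.145 × 0.855) = √0.30638 = 0.5535

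**Reproducing 424.** One-sided 0.05, 80% power: z_a = 1.6449, z_b = 0.8416.
n = [(0.9171 + 0.4658)/0.095]² = 211.92, total 423.8, so 424. This matches the plan exactly.

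**Two-sided 0.05, 80% power.** z_a = 1.9600.
n = [(1.0928 + 0.4658)/0.095]² = 269.19, total 538.4. With equal whole arms this is 270 per arm, or 540. The excess over the plan is 540 − 424 = 116, or 27%.

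**Two-sided 0.05, 70% power.** z_b = 0.5244.
n = [(1.0928 + 0.2903)/0.095]² = 211.96, total 423.9, also 424. The figure alone therefore cannot show how it was derived. The stated 80% fits only the one-sided calculation.

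**Other formulas, two-sided 80%.**

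| Formula | Total | Equal whole arms |
|---|---|---|
| Pooled variance | 538.4 | 540 |
| Unpooled variance | 532.9 | 534 |
| Arcsine | 533.2 | 534 |
| Continuity-corrected | 579.7 | 580 |

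None comes near 424. Unequal allocation does not help: 2:1 and 1:2 give two-sided totals of 591 and 621. Reading 424 as a per-arm number gives two-sided power of 94%, not 80%.

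**Power at fixed size.** Power = Φ[(d√n − z_a·A)/B]. At 212 per arm, d√n = 1.3832:
- one-sided: (1.3832 − 0.9171)/0.5535 = 0.842, power 80.0%
- two-sided: (1.3832 − 1.0928)/0.5535 = 0.525, power 70.0%

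| Total | One-sided 0.05 | Two-sided 0.05 |
|---|---|---|
| 424 | 80.0% (exact 80.4%) | 70.0% (exact 70.4%) |
| 500 | 85.5% (exact 85.7%) | 77.0% (exact 77.3%) |
| 540 | 87.8% | 80.1% |

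The exact values enumerate all outcomes of the uncorrected test.

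**Loss to follow-up (assumed; the plan gives no figure).** The 424 is stated as patients randomized. With 5%, 10%, 15% or 20% lost, two-sided power from 424 randomized is 68%, 65%, 63% or 60%. From 500 randomized it is 75%, 73%, 70% or 67%.

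**Bonferroni.** The plan does not say that the correction applies to this test. If it did, two-sided power at 424 would be 60% for two comparisons (alpha 0.025) and 49% for four (alpha 0.0125).

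**The case against.** The strongest reply is that nothing has been shown to be miscalculated. The hypothesis is directional, the hardware-removal aim is one of superiority, and 424 matches a one-sided 5% test to the patient. On that view a word is missing and the 70% belongs to a test the plan never named. Part of this stands: 424 is correct under the one-sided reading, and one-sided testing is a legitimate choice. But superiority is routinely tested two-sided, so the word does not settle the side, and the significance rule as written would let an analyst apply two-sided p below 0.05.

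The one-sided 80% also depends on the test chosen, which the plan leaves open. With a continuity correction, one-sided power at 424 is about 76% and about 466 patients are needed. That is fair, and it is why the uncorrected test is stated here as a condition.

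A further objection is that the 9.5-point difference is itself doubtful. Pain-related removals, medial and lateral together, are 22/126, and half of that is 11/126 = 8.7 points. That is a separate question about the inputs. It does not remove the ambiguity about the side, but it does mean that 540 answers only the stated 24% versus 14.5%.

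Lastly, the summary puts capacity at over 500, so 500 is not a strict ceiling.

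**Conclusion.** The concern holds. The plan does not state the side of its test, and its claim of 80% power at 424 patients is true only for one-sided alpha 0.05. Under the ordinary two-sided reading power is about 70%, the chance of missing the planned effect rises from 20% to about 30%, and 80% power needs about 540 evaluable patients (534 to 580 depending on formula).

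These figures rest on 24% versus 14.5%, 1:1 allocation and, apart from the 580, no continuity correction. They check the power sentence as written, which concerns removal for any reason using 6-month source rates. They are not the power for the primary objective in the study summary, which is framed as "reducing the incidence of hardware removal from the medial malleolus at one year after sustaining an ankle fracture". How the sponsor arrived at 424 cannot be known from the documents.

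**What to change.** State the side in the power statement and in both copies of the significance rule (Power Analysis and Statistics, and Statistical Methods in the study summary).

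- **If two-sided:** restate the power along these lines: *With 1:1 allocation, 424 evaluable patients give about 70% power at two-sided alpha 0.05 for 24% versus 14.5%; 80% power needs about 540 evaluable patients.*
- **If one-sided 0.05 is intended:** declare it in the same places, say that the whole 5% error lies on one side, and label the reported result as one-sided.
- **Either way:** name the test and the allocation ratio, say whether 424 counts randomized or evaluable patients, and give the loss allowance used.

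Declaring the side and restating the power at 424 costs only wording. Keeping 80% power with a two-sided test costs 116 more evaluable patients, above the estimated 500. If 5% to 20% were lost (an assumption), about 569 (540/0.95) to 675 (540/0.80) would have to be randomized.
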